## 7.3. Lost to Follow-Up

A participant will be considered lost to follow-up if he or she repeatedly fails to return for scheduled visits and is unable to be contacted by the study site. Site personnel or designee are expected to make diligent attempts to contact participants who fail to return for a scheduled visit or were otherwise unable to be followed up by the site.

Site personnel, or an independent third party, will attempt to collect the vital status of the participant within legal and ethical boundaries for all participants randomly assigned, including those who did not get IP. Public sources may be searched for vital status information. If vital status is determined to be deceased, this will be documented, and the participant will not be considered lost to follow-up. Sponsor personnel will not be involved in any attempts to collect vital status information.

## 8. Study Assessments and Procedures

- Study procedures and their timing are summarized in the SoA.
- Immediate safety concerns should be discussed with the sponsor immediately upon occurrence or awareness to determine if the participant should continue or discontinue study intervention.
- Adherence to the study design requirements, including those specified in the SoA, is essential and required for study conduct.
- All screening evaluations must be completed and reviewed to confirm that potential participants meet all eligibility criteria. The investigator will maintain a screening log to record details of all participants screened and to confirm eligibility or record reasons for screening failure, as applicable.

### 8.1. Efficacy Assessments

Not applicable.

### 8.2. Safety Assessments

Planned time points for all safety assessments are provided in the SoA.

Unless otherwise stated in the following subsections, all samples collected for specified laboratory tests will be destroyed within 60 days of receipt of confirmed test results. Certain samples may be retained for a longer period, if necessary, to comply with applicable laws, regulations, or laboratory certification standards.

#### 8.2.1. Physical Examinations

- A complete physical examination will be performed at screening and will include, at a minimum, assessments of the cardiovascular, respiratory, GI, dermatological, and neurological systems. Height and weight will also be measured and recorded at screening.
- Subsequent brief physical examination will include medical review and targeted, symptom-driven examination, as appropriate. Additional assessments may be performed at investigator's clinical discretion.

#### 8.2.2. Vital Signs

- For each participant, vital sign measurements should be conducted according to the SoA (Section 1.3).
- Blood pressure and pulse rate should be measured after at least 3 minutes supine.
- Unscheduled orthostatic vital signs should be assessed, if possible, during any AE of dizziness or posture-induced symptoms. Additional vital signs may be measured during each study period at investigator's discretion.

#### 8.2.3. Electrocardiograms

- For each participant, a single 12-lead ECG will be obtained as outlined in the SoA (see Section 1.3) and stored at site.

- Participants must be supine for at least 5 minutes before ECG collection, and remain supine but awake during procedure.
- ECGs may be obtained at additional times, when deemed clinically necessary. All ECGs recorded should be stored at the investigational site.
- Any clinically significant findings from ECGs that result in a diagnosis and that occur after the subject receives the first dose of the IP should be reported as an AE in the eCRF.
- ECGs will be interpreted by a qualified physician (the investigator or qualified designee) at the site as soon after the time of ECG collection as possible, and ideally while the subject is still present, to determine whether the subject meets entry criteria at the relevant visit(s) and for immediate subject management, should any clinically relevant findings be identified.
- If a clinically significant finding is identified (including, but not limited to, changes in QT/corrected QT interval from baseline) after enrollment, the investigator will determine if the participant can continue in the study. The investigator, or qualified designee, is responsible for determining if any change in participant management is needed, and must document his/her review of the ECG printed at the time of collection. Any new clinically relevant finding should be reported as an AE.

#### 8.2.4. Clinical Safety Laboratory Tests

- See Appendix 2 (Section 10.2) for the list of clinical laboratory tests to be performed and the SoA for the timing and frequency.
- The investigator must review the laboratory results, document this review, and report any clinically relevant changes occurring during the study as an AE. The laboratory results must be retained with source documents unless a Source Document Agreement or comparable document cites an electronic location that accommodates the expected retention duration. Clinically significant abnormal laboratory findings are those that are not associated with the underlying disease, unless judged by the investigator to be more severe than expected for the participant's condition.
- All laboratory tests with values considered clinically significantly abnormal during participation in the study should be repeated until the values return to normal or baseline or are no longer considered clinically significant by the investigator or medical monitor.
  - If such values do not return to normal/baseline within a period of time judged reasonable by the investigator, the etiology should be identified and the sponsor notified.
  - All protocol-required laboratory assessments, as defined in Appendix 2 (Section 10.2), must be conducted in accordance with the SoA, standard collection requirements, and laboratory manual.

- If laboratory values from nonprotocol-specified laboratory assessments performed at an investigator-designated local laboratory require a change in participant management or are considered clinically significant by the investigator (eg, SAE or AE or dose modification), then report the information as an AE.

## **Amylase and Lipase Measurements**

Serum amylase and lipase measurements will be collected as part of the clinical laboratory testing and as specified in the SoA (Section 1.3). Additional measurements may be performed at the investigator's discretion. Further diagnostic assessments will be recommended as per the algorithm (refer to Appendix 8) for the monitoring of pancreatic events whenever lipase and/or amylase is confirmed to be  $\geq 3$ x ULN at any visit postdose, even if the subject is asymptomatic.

### **8.2.5. Glucose Monitoring**

For safety purposes, plasma glucose measurements will be performed using a bedside glucose monitor as specified in the SoA (Section 1.3). Additional blood glucose monitor measurements may also be taken during the study as deemed necessary by the investigator where clinically indicated.

#### **8.2.5.1. Hypoglycemia Reporting**

Participants will be trained to recognize the signs, symptoms, and management of hypoglycemia, and to inform the investigator as soon as possible about these events. Participants may, at investigator's discretion, be given a glucometer to assist in the evaluation of these symptoms.

All hypoglycemic events will be captured in the eCRF as specified below:

- All hypoglycemic episodes will be recorded on a specific eCRF and should not be recorded as AEs unless the event meets serious criteria.
- If a hypoglycemic event meets severe criteria (see definition below), it should be recorded as serious on the AE and SAE eCRFs, and reported to Lilly as an SAE.

Investigators should use the following definitions and criteria when diagnosing and categorizing an episode considered to be related to hypoglycemia (the blood glucose values in this section refer to values determined by a laboratory or International Federation of Clinical Chemistry and Laboratory Medicine blood-equivalent glucose meters and strips) in accordance with the 2020 American Diabetes Association position statement on glycemic targets (ADA 2020) as below:

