### **2.3. Benefit/Risk Assessment**

As of 26 September 2022, tirzepatide (MOUNJARO) was approved in the US, EU, and Japan as an adjunct to diet and exercise to improve glycemic control in adults with T2DM. Risks of tirzepatide have been consistent with risks associated with other GLP-1 RAs that are currently marketed. Potential risks include, but are not limited to, GI effects, acute pancreatitis, increases in heart rate, and hypoglycemic events (GLP-1 RA class effect), which are all monitorable.

No clinically significant safety or tolerability concerns have been identified during clinical investigation of tirzepatide up to the highest single dose level of 8 mg or multiple weekly doses up to 15 mg, attained by stepwise dose escalation. The maximum tolerated dose as a single dose of tirzepatide in healthy participants was determined to be 5 mg. Based on this information, the 2x single 5-mg doses to be administered in Study GPIP are reasonably anticipated to be tolerable in this group of healthy participants.

There is no anticipated therapeutic benefit in these healthy participants.

More information about the known and expected benefits, risks, SAEs, and reasonably anticipated AEs of tirzepatide are to be found in the package insert of tirzepatide.

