### 3. Objectives and Endpoints

Objectives	Endpoints
Primary	

 
To evaluate the bioequivalence between the MUPFP (test) and the SDP (reference), as assessed using tirzepatide PK in healthy participants
 
	
 
<math>C_{max}</math>, <math>AUC_{(0-t)}</math>, <math>AUC_{(0-\infty)}</math>
 

Secondary	

 
To evaluate the additional PK parameter
 
To evaluate the safety and tolerability of a single subcutaneous dose of tirzepatide administered through MUPFP (test) versus SDP (reference)
 
	
 
<math>t_{max}</math>
 
Incidence of AEs
 

Abbreviations: AE = adverse event;  $AUC_{(0-t)}$  = area under the concentration versus time curve from time zero to time  $t$ ;  $AUC_{(0-\infty)}$  = area under the concentration versus time curve from zero to infinity;  $C_{max}$  = maximum observed drug concentration; MUPFP = multi-use prefilled pen; PK = pharmacokinetics; SDP = single-dose pen;  $t_{max}$  = time of maximum observed drug concentration.

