#### **Level 2 hypoglycemia:**

**Glucose  $<54$  mg/dL (3.0 mmol/L):** This is also referred to as documented or blood glucose confirmed hypoglycemia with glucose  $<54$  mg/dL (3.0 mmol/L). This glucose threshold is clinically relevant regardless of the presence or absence of symptoms of hypoglycemia.

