### **8.3.3. Adverse Events of Special Interest**

AEs of special interest for this program include:

- pancreatitis
- major adverse cardiovascular events
- deaths
- hypoglycemia (Level 2 and 3)
- thyroid malignancies and C-cell hyperplasia
- supraventricular arrhythmias and cardiac conductive disorders
- hypersensitivity events
- severe ISRs, and
- severe GI AEs

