4.5.4. Hypoglycemic Events

Hypoglycemic events will be appropriately recorded in the CRF. Hypoglycemic events are defined as follows:

Table 3. Hypoglycemic events

Category	Glucose
Level 1 hypoglycemia	<70 mg/dL (3.9 mmol/L) and \geq 54 mg/dL (3.0 mmol/L)
Level 2 hypoglycemia	<54 mg/dL (3.0 mmol/L)
Level 3 (Severe) hypoglycemia	N/A
Nocturnal hypoglycemia	N/A

Severe hypoglycemia is a severe event characterized by altered mental and/or physical status requiring assistance for treatment of hypoglycemia. Details can be found in the protocol.

Nocturnal hypoglycemia is a hypoglycemic event (including severe event) that occurred at night and presumably during sleep –between bedtime and waking.

Hypoglycemic events will be listed.

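### Non-serious hypoglycemia, including Level 2, is missing from the by-device adverse event incidence, and no other planned table counts it

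*Protocol*

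**What the plan says.** **Objective and endpoint.** Protocol Section 3 and SAP 1.1 set a secondary objective, "To evaluate the safety and tolerability of a single subcutaneous dose of tirzepatide administered through MUPFP (test) versus SDP (reference"), with AE incidence as its endpoint. Protocol 2.3 gives the potential risks as "GI effects, acute pancreatitis, increases in heart rate, and hypoglycemic events (GLP-1 RA class effect), which are all monitorable".

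**Recording.** Protocol 8.2.5.1 sends every hypoglycemic episode to a form of its own and says that episodes "should not be recorded as AEs unless the event meets serious criteria". For an episode that meets the severe criteria, "it should be recorded as serious on the AE and SAE eCRFs, and reported to Lilly as an SAE". Level 2 is defined by glucose below 54 mg/dL alone, and the protocol adds: "This glucose threshold is clinically relevant regardless of the presence or absence of symptoms of hypoglycemia".

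**Special interest.** Protocol 8.3.3 includes "hypoglycemia (Level 2 and 3") in its list of adverse events of special interest.

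**Analysis.** SAP 4.5.2 summarizes treatment-emergent AEs by treatment, with counts and percentages by system organ class and preferred term. SAP 4.5.4 defines the hypoglycemia levels and then says only: "Hypoglycemic events will be listed". SAP 4.1 confines summary statistics to data for which the SAP details them, and SAP Section 1 gives the SAP precedence over the protocol's statistical section.

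**The concern.** The device comparison of safety rests on AE incidence, and the AE records exclude one kind of event by rule. Hypoglycemia is one of the four risks that the benefit/risk section names. The protocol schedules bedside glucose readings and provides a dedicated form for episodes, but the SAP never turns that form into a count by device. A reader who relies on the treatment-emergent AE table for the device comparison would see serious hypoglycemia only, and the plan calls for no note saying so.

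There is also a mismatch in classification. A non-serious Level 2 event is an adverse event of special interest under one section and is not to be recorded as an adverse event under another.

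**Working it through.** The plan states no figure for hypoglycemia, so there is none to reproduce. The check is mainly a matter of tracing each kind of event through the documents.

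**Step 1: where each event goes.**

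| Event | AE form (Protocol 8.2.5.1) | Special interest (8.3.3) | By-device AE table (SAP 4.5.2) | Listing (SAP 4.5.4) |
|---|---|---|---|---|
| Level 1, non-serious | No | No | No | Yes |
| Level 2, non-serious | No | Yes | No | Yes |
| Level 2, serious | Yes | Yes | Yes | Yes |
| Level 3 | Yes, as serious | Yes | Yes | Yes |

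Level 2 is defined by a glucose value, so it is not serious by definition. The second row is the one in which the sections disagree.

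**Step 2: is the count planned elsewhere?**
- Protocol 9.3.4 names AEs, safety laboratory parameters and vital signs as the safety parameters.
- SAP 4.5.8 lists out-of-range laboratory values without summarizing them.
- No SAP section covers the bedside glucose readings.
- The allowances for further analyses in Protocol 9.3.4 and SAP 4.1 do not prespecify a count.

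No planned table gives hypoglycemia by device.

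**Step 3: comparison with injection-site reactions.** Under Protocol 8.2.6 these are recorded as AEs and also on a dedicated form. SAP 4.5.7 then both lists them and tabulates them by treatment. Non-serious hypoglycemia gets neither the AE record nor the table, and the documents give no reason for the difference.

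**Step 4: how much monitoring there is.** The Schedule of Activities has glucose readings at predose, 12, 24, 36, 48 and 72 hours in each period: 6 readings, 5 of them postdose. With 54 completers:
- all scheduled readings: 6 x 2 x 54 = 648
- postdose readings: 5 x 2 x 54 = 540

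Only the 540 bear on events after dosing.

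**Step 5: scale, by assumption only.** Let p be the assumed proportion of participants with a non-serious Level 2 event after one dose, and n the number dosed per device, from 54 (completers) to 65 (enrolled). The expected number affected is n x p, and the chance of at least one is 1 - (1 - p)^n.

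| Assumed p | Expected per device, n = 54 to 65 | Chance of at least one |
|---|---|---|
| 1% | 0.5 to 0.7 | 42% to 48% |
| 2% | 1.1 to 1.3 | 66% to 73% |
| 5% | 2.7 to 3.3 | 94% to 96% |
| 10% | 5.4 to 6.5 | above 99% |

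For example, 54 x 0.02 = 1.08 and 1 - 0.98^54 = 0.664. Under Protocol 8.2.5.1 none of these participants would enter the by-device AE table on account of the hypoglycemia. The rates are illustrations and come from no document.

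**The case against.** The strongest defense is that nothing is lost. Every episode is captured on a form, the levels are defined in the SAP, and all events are listed. In a two-period crossover with 54 to 65 participants, a few events can be counted by hand from the listing. The endpoint is secondary and descriptive, with no test or decision rule. Both periods give 5 mg of the same drug, and the documented differences are the device and the volume (0.6 versus 0.5 mL). A device effect on glucose would be expected to act through exposure, which the primary Cmax and AUC comparison assesses directly. Listing sparse events rather than tabulating them is partly a matter of presentation.

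Most of this stands, and it limits the weight of the point. It does not remove the gap: the stated endpoint is an incidence, and a listing is not one.

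A reader might infer four stronger things that the documents do not support:
- **That Protocol 8.2.5.1 and 8.3.3 cannot both be followed.** Section 8.3.3 is a list of topics. It prescribes no form, route or analysis, and the event-collection table in 8.3.1 has no row for events of special interest. A site can follow 8.2.5.1 without breaching 8.3.3. The conflict is one of classification.
- **That a special-interest table would be incomplete.** The SAP plans no such table. The omission is from the general treatment-emergent AE table.
- **That hypoglycemia as a whole is left out.** Level 3 and any other serious events are included.
- **That every scheduled low reading is a missing event.** Section 8.2.5.1 applies the levels to episodes considered related to hypoglycemia, which leaves room for the investigator's judgment.

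**Conclusion.** The point holds for non-serious events. As written, the by-device AE incidence that answers the secondary safety objective contains no Level 1 and no non-serious Level 2 hypoglycemia, and no other planned table supplies the count. The gap is in summary and comparison; collection is complete. How many participants it concerns cannot be derived from the documents, which give no hypoglycemia rate. The bioequivalence conclusion is untouched. This is a modest fault in the completeness of a descriptive endpoint, worth correcting because the data will already be in hand.

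**What to change.** 1. In SAP 4.5.4, state that postdose hypoglycemic events will be listed and also summarized by device and Level (number of events, number and percentage of participants), in the way SAP 4.5.7 already treats injection-site reactions.
2. Footnote the treatment-emergent AE table to say that non-serious hypoglycemia is reported in that summary.
3. Reconcile Protocol 8.2.5.1 and 8.3.3 so that both describe the classification and recording of Level 2 events in the same way. Which route to adopt is for the sponsor to decide.

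The cost is one table from data already on the hypoglycemia eCRF, one footnote and one clarifying sentence in the protocol. The downside is that asymptomatic low readings in healthy participants may appear as counts; showing the Levels separately lets a reader weigh them. No dose, visit or clinical rule changes.

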#### **Level 1 hypoglycemia:**

**Glucose  $<70$  mg/dL (3.9 mmol/L) and  $\geq 54$  mg/dL (3.0 mmol/L):** Level 1 hypoglycemia can alert a person to take action such as treatment with fast-acting carbohydrates. Providers should continue to counsel participants to treat hypoglycemia at this glucose alert value.

#### **Level 2 hypoglycemia:**

**Glucose  $<54$  mg/dL (3.0 mmol/L):** This is also referred to as documented or blood glucose confirmed hypoglycemia with glucose  $<54$  mg/dL (3.0 mmol/L). This glucose threshold is clinically relevant regardless of the presence or absence of symptoms of hypoglycemia.

**Level 3 hypoglycemia:**

**Severe hypoglycemia (in adults):** A severe event characterized by altered mental and/or physical status requiring assistance for treatment of hypoglycemia. For example, participants had altered mental status, and could not assist in their own care, or were semiconscious or unconscious, or experienced coma with or without seizures, and the assistance of another person was needed to actively administer carbohydrate, glucagon, or other resuscitative actions. Glucose measurements may not be available during such an event, but neurological recovery attributable to the restoration of glucose concentration to normal is considered sufficient evidence that the event was induced by a low glucose concentration.

- The determination of a hypoglycemic event as an episode of severe hypoglycemia, as defined above, is made by the investigator based on the medical need of the participant to have required assistance and is not predicated on the report of a participant simply having received assistance.
- If a hypoglycemic event meets the criteria of severe hypoglycemia, the investigator must record the event as serious on the AE CRF and report it to Lilly as an SAE.

**Nocturnal hypoglycemia:**

Nocturnal hypoglycemia is a hypoglycemia event (including severe hypoglycemia) that occurs at night and presumably during sleep.

**8.2.6. Injection-Site Reactions**

Symptoms and signs of a local ISR may include erythema, induration, pain, pruritus, and edema. If an ISR is reported by a participant or assessed as clinically significant by site personnel, this shall be recorded as an AE and the ISR CRF will be used to capture additional information about this reaction, such as injection-site pain, degree and area of erythema, induration, pruritus, and edema.

**8.2.7. Hypersensitivity Reactions**

All hypersensitivity reactions will be reported by the investigator as either AEs or, if any serious criterion is met, as SAEs.

In the event of suspected drug hypersensitivity reactions (immediate or nonimmediate) in participants who experience moderate-to-severe injection reactions as assessed by the investigator, unscheduled blood samples will be collected for PK at the following time points:

- as close as possible to the onset of the event
- at the resolution of the event
- 30 ( $\pm 3$ ) days following the event.

Instructions for the collection and handling of blood samples will be provided by the sponsor. The actual date and time (24-hour clock time) of each sampling will be recorded.

**8.2.8. Safety Monitoring**

The Lilly CP or CRP/scientist will monitor safety data throughout the course of the study.

Lilly will review SAEs within time frames mandated by company procedures. The Lilly CP or CRP will periodically review the following data:

- trends in safety data
- laboratory analytes including glucose, amylase, and lipase
- serious and nonserious AEs, including AEs of interest.

Further diagnostic assessments will be recommended whenever lipase and/or amylase are confirmed to be  $\geq 3$ x ULN at any visit postdose even if the subject is asymptomatic.

When appropriate, the Lilly CP or CRP will consult with the functionally independent Global Patient Safety therapeutic area physician or clinical research scientist.

### 8.2.8.1. Hepatic Safety

#### Close hepatic monitoring

Laboratory tests (Appendix 7 [Section 10.7]), including ALT, AST, ALP, TBL, direct bilirubin, gamma-glutamyl transferase, and creatine kinase, should be repeated within 48 to 72 hours to confirm the abnormality and to determine if it is increasing or decreasing, if 1 or more of these conditions occur:

If a participant with baseline results of...	develops the following elevations:
ALT or AST $< 1.5$ x ULN	ALT or AST $\geq 3$ x ULN
ALP $< 1.5$ x ULN	ALP $\geq 2$ x ULN
TBL $< 1.5$ x ULN	TBL $\geq 2$ x ULN (except for patients with Gilbert's syndrome)
ALT or AST $\geq 1.5$ x ULN	ALT or AST $\geq 2$ x baseline
ALP $\geq 1.5$ x ULN	ALP $\geq 2$ x baseline
TBL $\geq 1.5$ x ULN	TBL $\geq 1.5$ x baseline (except for patients with Gilbert's syndrome)

If the abnormality persists or worsens, clinical and laboratory monitoring, and evaluation for possible causes of abnormal liver test results should be initiated by the investigator in consultation with the Lilly-designated medical monitor. At a minimum, this evaluation should include physical examination and a thorough medical history, including symptoms, recent illnesses (eg, heart failure, systemic infection, hypotension, or seizures), recent travel, history of concomitant medications (including over the counter), herbal and dietary supplements, history of alcohol drinking and other substance abuse.

Initially, monitoring of symptoms and hepatic biochemical tests should be done at a frequency of 1 to 3 times weekly, based on the participant's clinical condition and hepatic biochemical tests. Subsequently, the frequency of monitoring may be lowered to once every 1 to 2 weeks, if the participant's clinical condition and laboratory results stabilize. Monitoring of ALT, AST, ALP, and TBL should continue until levels normalize or return to approximate baseline levels.

